5.3.5.7 Deaths

For this protocol, mortality from any cause and mortality from respiratory diseases are included as efficacy endpoints. Mortality is also included as part of the PFS efficacy endpoint. Deaths that occur during the protocol-specified adverse event reporting period (see Section 5.3.1) that are attributed by the investigator solely to progression of unclassifiable ILD should be recorded on the Death Attributed to Progressive Disease eCRF. All other on-trial deaths, regardless of relationship to trial treatment, must be recorded on the Adverse Event eCRF and immediately reported to the Sponsor (see Section 5.4.2). The iDMC will monitor the frequency of deaths in this trial.

Death should be considered an outcome and not a distinct event. The event or condition that caused or contributed to the fatal outcome should be recorded as the single medical concept on the Adverse Event eCRF. Generally, only one such event should be reported.

The term "**sudden death**" should be used only for the occurrence of an abrupt and unexpected death due to presumed cardiac causes in a patient with or without pre-existing heart disease, within 1 hour after the onset of acute symptoms or, in the case of an unwitnessed death, within 24 hours after the patient was last seen alive and stable. If the cause of death is unknown and cannot be ascertained at the time of reporting, "**unexplained death**" should be recorded on the Adverse Event eCRF. If the cause of death later becomes available (e.g., after autopsy), "unexplained death" should be replaced by the established cause of death.

Deaths that occur after the adverse event reporting period should be reported as described in Section 5.6.

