5.3.5.9 Lack of Efficacy or Worsening of Unclassifiable ILD

Events that are clearly consistent with the expected pattern of progression of the underlying disease should not be recorded as adverse events. These data will be captured as efficacy assessment data only. In most cases, the expected pattern of progression will be based on $\geq 10\%$ relative decline in FVC or a >50 m decline in 6MWD. In rare cases, the determination of clinical progression will be based on symptomatic deterioration or a decline in DLco of $\geq 15\%$. However, every effort should be made to document progression through use of objective criteria. If there is any uncertainty as to whether an event is due to disease progression, it should be reported as an adverse event.

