2.3 DETERMINATION OF SAMPLE SIZE

The purpose of this trial is hypothesis generation regarding the efficacy of pirfenidone vs. placebo on lung function parameters on the basis of rate of decline in FVC, as measured by daily handheld spirometry.

A total sample size of approximately 250 patients is planned, and patients will be randomized in a 1:1 ratio. The randomization will be stratified by concomitant MMF treatment (yes/no), the presence/absence of IPAF as defined by the MDT.

The planned sample size is based on the statistical hypothesis of the primary endpoint and assumes 80% power and a two-sided significance level of 5% using a student's t-test. It is assumed, after inspection of historical data, that FVC decline in the placebo arm is 85 mL with a common standard deviation of 70 mL, which can be reduced to 60 mL with a common standard deviation of 70 mL in the pirfenidone arm. In this

Pirfenidone — F. Hoffmann-La Roche Ltd

scenario, 125 patients per treatment arm are needed to detect this treatment effect with 80% power.

These assumptions are based upon the following considerations: in IPF, the annual rate of decline of FVC is approximately 200 mL. Owing to the fact that patients with unclassifiable ILD have rates of disease progression in the range of patients with IPF, albeit with a lower mortality rate (Ryerson et al. 2013), a similar decline rate of 200 mL/year, equivalent to a 100 mL decline over a treatment period of 24 weeks, can be expected. However, a yet unknown proportion of patients in this trial will be treated concomitantly with MMF. In a previous study of CTD-ILD (Fischer et al. 2013), MMF was found to have beneficial effects on lung functions in these patients. While CTD-ILD is a distinct entity from the current trial population, both conditions may share some autoimmune features. Therefore, assuming a smaller FVC decline of 85 mL in the placebo arm compared with 60 mL in the pirfenidone arm over the 24-week double-blind treatment period appears justified. In addition, the potential confounding effect of concomitant MMF therapy in these patients justifies stratification to ensure equal distribution of patients who receive and do not receive treatment with MMF.

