- Progression free survival (PFS), defined as the time to the first occurrence of a >10% absolute decline in percent predicted FVC, a >50 m decline of 6MWD, or death from any cause, will be analyzed using Kaplan-Meier techniques:
 - KM plots of time to first occurrence of the combined primary efficacy endpoint will be provided by treatment arm.
 - Frequencies and percentages of patients with events and patients censored will be provided. Descriptive statistics of KM estimates of PFS (weeks) will be presented.
 - The PFS of two randomized treatment arms will be compared with a logrank test.
 - Hazard ratios and corresponding 95% CI will be calculated by applying Cox-proportional hazard models.
- An alternative definition of PFS (also in weeks), namely the time to the first occurrence of a >10% relative decline in FVC, non-elective respiratory hospitalization, or death, will be analyzed using Kaplan-Meier techniques as Pirfenidone — F. Hoffmann-La Roche Ltd

- defined for the point above; and the two treatment arms will be compared with a log-rank test. In addition, hazard ratios and corresponding 95% CI will be calculated by applying Cox-proportional hazard models
- Time to death from any cause and time to death from respiratory diseases
 assessed by the SOC "Respiratory, thoracic and mediastinal disorders" (in weeks)
 will be analyzed using Kaplan-Meier techniques as defined above; and the two
 treatment arms will be compared with a log-rank test. In addition, hazard ratios
 and corresponding 95% CI will be calculated by applying Cox-proportional
 hazard models.

For all secondary endpoints p-values will be reported in a descriptive fashion. No multiplicity adjustments for statistical testing will be done.

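### Respiratory death is identified only by a MedDRA SOC, which on the most natural reading leaves deaths recorded on the progressive-disease death form without a route into the endpoint

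*SAP*

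**What the plan says.** SAP version 3.0, section 4.5.3, analyses time to death from respiratory diseases by Kaplan-Meier, log-rank and Cox methods. The event is "assessed by the SOC 'Respiratory, thoracic and mediastinal disorders' (in weeks". Version 2.0 (section 4.5.2) has the same rule. Neither version adds an adjudication step, a source form or a second criterion. SAP 4.5.4 uses respiratory deaths again in the MMF subgroup analysis.

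Protocol 5.3.5.7 states that "mortality from any cause and mortality from respiratory diseases are included as efficacy endpoints". It then sets two recording routes for deaths in the adverse event reporting period. Deaths "attributed by the investigator solely to progression of unclassifiable ILD should be recorded on the Death Attributed to Progressive Disease eCRF". The next sentence reads: "All other on-trial deaths, regardless of relationship to trial treatment, must be recorded on the Adverse Event eCRF".

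On coding, SAP 4.6.2 maps adverse event terms to preferred term and SOC, and SAP 4.4.3 does so for medical history. The SAP describes SOC coding for nothing else.

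**The concern.** A reader of a respiratory-mortality result will take it to include deaths from the lung disease under study. If the SOC rule is fed only by adverse event records, a death that the investigator blames entirely on that disease carries no SOC and drops out, while a respiratory death with a less certain cause is counted. The endpoint would then miss the deaths it most obviously should contain. This would affect the time-to-event analysis in SAP 4.5.3 and the MMF subgroup analysis in SAP 4.5.4.

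**Working it through.** There is no arithmetic to do. The plan gives no expected number of respiratory deaths and the documents give no observed one. The check follows a death from the form to the endpoint.

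1. **Criterion.** SAP 4.5.3: the SOC, and nothing else.
2. **What receives a SOC.** SAP 4.6.2 (adverse events) and SAP 4.4.3 (medical history). Medical history cannot supply a cause of death on trial, so the adverse event record is the only described source.
3. **What reaches the adverse event record.** Protocol 5.3.5.7 sends every on-trial death there except those attributed solely to ILD progression, which have their own form.
4. **Does progression reach the adverse event record some other way?** Protocol 5.3.5.9 says that events clearly matching expected progression are not adverse events: "These data will be captured as efficacy assessment data only". Protocol 5.3.5.10 likewise does not treat a hospitalization due only to ILD progression as an adverse event. Neither passage mentions deaths. They fit the two-route reading but do not settle how a progression death is classified.
5. **Does the SAP pick up the separate form elsewhere?** It is not named in either version. SAP 4.6.3 counts deaths by arm without limiting them to adverse events, and lists the death information from the study discontinuation panel. It assigns no SOC and no respiratory cause, so it does not feed the endpoint.
6. **Which analyses use the SOC rule?** Respiratory death in SAP 4.5.3, and its reuse in SAP 4.5.4. Time to death from any cause and the death component of both PFS definitions do not.

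Put side by side, steps 1 to 3 leave a progression-only death with no described path to a SOC, and step 5 offers no alternative path. On intent, the direct evidence is Protocol 5.3.5.7 itself, which makes respiratory mortality an efficacy endpoint in the same section that creates the separate form.

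Several provisions keep the number of affected deaths small:
- Only deaths attributed solely to progression take the separate route.
- Protocol 5.3.5.9 sends doubtful events to the adverse event record: "If there is any uncertainty as to whether an event is due to disease progression, it should be reported as an adverse event".
- SAP 4.1.1 ends the efficacy period at completion or early discontinuation of double-blind treatment.
- SAP 4.5.8 describes deaths as low in number.

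**The case against.** The strongest reply is that the harm is read out of silence. SAP 4.5.3 names no source form, and no passage says that the progression form is uncoded or excluded. A cause from that form could have been coded in a step the SAP does not describe. This stands. A reader might infer that the SAP excludes progression deaths; the documents support only that it gives no route for including them.

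The second reply comes from Protocol 5.3.5.7 itself. Its next paragraph says that the condition causing or contributing to a death is to be entered as one concept on the Adverse Event eCRF, and it makes no exception for progression. Read alone, that puts the cause of every death where SAP 4.6.2 would give it a SOC. It is real contrary text. I give it less weight because it follows directly on the paragraph that separates the two routes, and applying it to progression-only deaths would leave the separate form with little purpose. The protocol is nevertheless ambiguous here.

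The third reply is that little depends on the endpoint: secondary p-values are descriptive, no multiplicity adjustment is made, and the SAP says of the trial: "The purpose of this trial is hypothesis generation regarding the efficacy of pirfenidone vs. placebo". The deaths also stay visible in SAP 4.6.3 and in all-cause mortality. This stands too, and it sets the severity. It does not remove the point, because respiratory death is reported as an endpoint with its own curves, test and hazard ratio.

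**Conclusion.** Wrong as written, minor severity. The SOC is the only stated criterion for respiratory death, and on the most natural reading of the protocol it does not reach deaths recorded on the Death Attributed to Progressive Disease eCRF. The conclusion assumes that the two recording routes in Protocol 5.3.5.7 are exclusive and that SOC coding is confined to the data for which the SAP describes it.

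The size cannot be stated. The number of affected deaths is not in the documents and may be zero.

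Two stronger readings are tempting and are not supported. One is that the respiratory-death result already produced is an undercount: the documents do not say which source the March 2019 analysis used. The other is that the gap favours one arm or weakens the mortality findings generally: nothing gives deaths by arm or by form, and all-cause death and both PFS definitions do not use the SOC rule.

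**What to change.** In SAP 4.5.3, and by reference in 4.5.4, define a respiratory death as either (a) any death recorded on the Death Attributed to Progressive Disease eCRF, or (b) any death recorded on the Adverse Event eCRF whose cause codes to the respiratory SOC.

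What follows depends on the March 2019 analysis noted in SAP 4.5.8. If it used AE-coded deaths only, label the revised definition post hoc and report both results. If it already included deaths from the progression form, state that source; no second result is needed.

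The cost is one definition and one derivation, plus a second set of respiratory-death outputs in the first case only. The protocol already provides for both forms, so no new data collection should be needed. The fields on the progression form are not shown in the documents, so that should be confirmed.

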4.5.4 Exploratory Efficacy Endpoints

The exploratory objectives for this trial are to evaluate the role of MMF treatment in ILD and to investigate potential biomarkers associated with fibrosis and ILD.

For the MMF objective, primary and selected secondary endpoints will be investigated by means of a subgroup analyses that stratifies patients according to whether they received MMF treatment. In addition, the overall safety summary will be presented by this subgroup. The selected secondary endpoints are:

- Deaths from any cause and respiratory disease-related
- Hospitalizations from any cause and respiratory disease-related

The analysis of these exploratory efficacy endpoints by subgroup are defined under section Section 4.5.6.

The mean FVC decline in each treatment arm will be calculated as in the primary analysis for the subgroups of patients that received MMF treatment and compared using a student's t-test.

Other exploratory efficacy endpoints are discussed in the sensitivity and subgroup sections (see Section 4.5.6 and Section 4.5.7, respectively).

Moreover, additional categorical analyses for the percent predicted DLco and 6MWD will be presented as exploratory:

- Categorical change of >15% absolute decline from baseline to week 24 in percent predicted DLco will be compared between the treatment arms using a logistic regression.
- Categorical change of >50% absolute decline from baseline to week 24 in 6MWD
 (m) will be compared between the treatment arms using a logistic regression.

Pirfenidone — F. Hoffmann-La Roche Ltd

For the biomarker objective, assessments of the exploratory biomarkers and their relationship with drug responses will be described in a separate analysis plan.

A correlation analysis of individual patient slopes estimated by linear regression models between those obtained for home spirometry and site spirometry were performed to assess the concordance of the data obtained by the two methods.

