
 To evaluate the safety of pirfenidone vs. placebo 	
 Nature, frequency, severity, and timing of treatment-emergent adverse events Dose reductions and treatment interruptions Clinical laboratory test results 12-lead ECGs Withdrawals from trial treatment or trial discontinuations
Exploratory Objectives:	

 To evaluate the role of MMF treatment in ILD 	
 Efficacy and safety data from subgroups of patients who did or did not receive MMF treatment

 To evaluate potential biomarkers associated with fibrosis and ILD 	
 Biomarker data from plasma, serum, and whole blood RNA and DNA samples

6MWD=6-minute walk distance; DLco=diffusing capacity of the lung for carbon monoxide; DNA=deoxyribonucleic acid; ECG=electrocardiogram; FVC=forced vital capacity; ILD=interstitial lung disease; MMF=mycophenolate mofetil/sodium or mycophenolic acid; PFS=progression-free survival; PRO=patient-reported outcome; RNA=ribonucleic acid; SGRQ=St. George's Respiratory Questionnaire; SOBQ=Shortness of Breath Questionnaire; UCSD=University of California, San Diego

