6.6 EXPLORATORY ANALYSES

The exploratory objectives for this trial are to evaluate the role of MMF treatment in ILD and to investigate potential biomarkers associated with fibrosis and ILD (see Section 2).

For the MMF objective, efficacy and safety data will be investigated by means of a subgroup analyses that stratifies patients according to whether they received MMF treatment. The conduct of these analyses will be described in detail in the Statistical Analysis Plan (SAP).

For the biomarker objective, assessments of the exploratory biomarkers and their relationship with drug responses will be described in a separate analysis plan.

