A summary table displaying the mean FVC decline together with two-sided 95% confidence intervals based on percentiles of the t-distribution will be provided by treatment arm. The mean FVC decline in each treatment arm will be compared using a student's t-test with a two-sided significance level α =0.05. Additionally, a two sample Wilcoxon test will be used for treatment comparison. Results of this test are of descriptive nature only.

The same analyses will be done by restricting the FVC decline values:

- Including patients with at least 3 site spirometry measurements Pirfenidone — F. Hoffmann-La Roche Ltd

- excluding patients with a predicted FVC decline below -1000 mL
- or above 1000 mL
- excluding values with a difference +/-50% from corresponding baseline site spirometry

Mean FVC declines and results from Student's t-test by subgroups (for definition see 4.5.6) will be displayed in a forest plot.

As a sensitivity analysis to the primary analysis, the time-adjusted mean FVC decline will be estimated by a repeated measures mixed model with patient effects fitted as random and day of measurement and treatment fitted as fixed effects. Please refer to Section 4.5.6 for further details.

A detailed description of SAS code to be used for the repeated measures mixed model is provided together with the respective table shell.

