4.5.6 Sensitivity Analyses

As a sensitivity analysis to the primary analysis, the time-adjusted mean FVC decline will be estimated a random slope and intercept linear regression model, with an absolute change in FVC (mL) as the outcome variable assuming linear decline in lung function over time. The model includes random coefficients for slope and intercept and fixed effect terms for treatment, and covariates to be selected as described below. The statistical model is defined as follows:

$$Y_{ijk} = (\alpha + a_i) + (\gamma + \beta_s T_k + g_i) t_{ij} + \beta_g Cov 1_i + \beta_a Cov 2_i + \epsilon_{ij}$$

- o Y_{ijk} is the value measured for ith patient at time j in treatment group k
- o t_{ij} is the time of measurements for ith patient at study day j
- \circ T_k =0 if patient in Placebo group and T_k=1 is patient in Pirfenidone
- \circ β_s is the effect of Pirfenidone on the slope
- \circ α and γ are elements of the intercept and slope respectively a_i and g_i are random specific components of the intercept and slope for the ith patient
- \circ β_g , β_a are patient specific demographics' coefficients (strata)
- o Cov1_i, Cov2_i are covariates to be included for the ith patient
- ο ε_{ii} is the random error for ith patient at time j
- o a_i and g_i are assumed to be normally distributed with mean 0 and arbitrary covariance matrix
- \circ ε_{ij} are assumed to be independent and normally distributed with mean 0 and variance σ ε²
- Within patient errors follow a random coefficient regression model with random effect for intercept and slope
- An unstructured variance-covariance structure will be used to model the within patient measurements
- The variance-covariance matrix, modeled to estimate the inter-individual variability is considered to have a Variance-Components structure

The model will be applied by adding the stratification factors MMF treatment and IPAF as covariates to the home spirometry data, once taking into account the old and once the new quality flag.

The same model with and without adding the stratification factors as covariates will be applied to the key secondary endpoint of site-measured FVC (mL).

Pirfenidone — F. Hoffmann-La Roche Ltd

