4.5.7 Subgroup Analyses

Subgroup analyses will be conducted for the exploratory endpoint, as described in Section 4.5.4. The following subgroups will be based on:

- The four groups resulting from combinations of the two stratification factors:
 - Concomitant MMF treatment (yes/no)
 - o Presence/absence of IPAF as defined by the MDT
- Gender: Male, Female
- Age (years): <65 years, ≥ 65 years
- Percent predicted FVC at Baseline: <65%, ≥65% to < 80%, ≥80%
- Percent predicted DLco at Baseline: <35%, ≥35%
- Body weight: <60 kg, ≥60 kg
- Previous Biopsy (yes/no)

4.5.8 Sensitivity Analyses for missing data

The robustness of the primary method of estimation described above will be explored by a series of sensitivity estimators based on varying assumptions underlying the multiple imputation strategy.

As the primary analysis for this study was performed in March 2019 the number of patients with missing FVC values at week 24 are known. No data was collected after treatment discontinuation.

3 different approaches will be used to evaluate the robustness of the analysis of the secondary endpoint to the missing at random (MAR) assumption.

Due to the low number, deaths and other intercurrent events have not been considered in the multiple imputation analysis.

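### The exploratory MMF objective rests on tests within subgroups, and the plan never estimates how the pirfenidone effect differs with and without MMF

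*SAP*

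**What the plan says.** Protocol Section 2, Table 1, sets an exploratory objective: "To evaluate the role of MMF treatment in ILD". Its endpoint is efficacy and safety data in patients with and without MMF. Protocol 6.6 leaves the method to the SAP: "The conduct of these analyses will be described in detail in the Statistical Analysis Plan".

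The current SAP (version 3.0) provides the following:

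- **4.5.4:** the primary and selected secondary endpoints are examined "by means of a subgroup analyses that stratifies patients according to whether they received MMF treatment". FVC decline is compared between arms by Student's t-test "for the subgroups of patients that received MMF treatment". Deaths, hospitalizations and the overall safety summary are also to be shown by MMF.
- **4.5.1 and 4.5.3:** for home and site FVC, mean declines and t-test results "by subgroups (for definition see 4.5.6) will be displayed in a forest plot".
- **4.5.7:** the subgroup list brings in MMF through "The four groups resulting from combinations of the two stratification factors", that is, MMF crossed with IPAF.
- **4.5.6:** "The model will be applied by adding the stratification factors MMF treatment and IPAF as covariates". In the displayed equation these covariates shift the level of FVC; only treatment modifies the slope.
- **4.5.8:** the only interaction named is treatment by time.

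Sections 4.5.1, 4.5.3 and 4.5.4 all send the reader to 4.5.6 for the subgroup definitions. In version 3.0 that section holds the sensitivity analyses, and the subgroups are in 4.5.7.

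**The concern.** A natural question under this objective is whether the pirfenidone effect depends on MMF. That is a difference between two treatment effects, with its own estimate and standard error. The plan gives an effect and a test inside each subgroup and stops there.

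A reader left to compare two verdicts can easily take one significant and one non-significant result as effect modification. With modest power in each subgroup, such a split is common when the effects are equal. Unequal subgroup sizes make it more likely, and the sample size section says the share on MMF is not known.

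**Working it through.** **Inputs.** From Protocol 6.1 and SAP 2.3: declines of 85 and 60 mL (difference 25 mL), common SD 70 mL, 125 per arm, 1:1 allocation. Assumed: the MMF share (10% to 50%), and a two-sided 5% level, because SAP 4.5.4 in version 3.0 states none. The matching section of SAP version 2.0 (4.5.3) used 0.05. No dropout is applied.

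**The plan's own figure.** Normal approximation: n = 2 × (1.960 + 0.842)² × (70/25)² = 123.1, so 124 per arm. The exact noncentral t needs 124.04, so 125. Power at 125 is 80.3%. The stated 125 is reproduced.

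**Power within subgroups.** The noncentrality is (25/70) × √(n/2) with 2n − 2 degrees of freedom. Let a be the power with MMF and b the power without, under the same true 25 mL effect. The tests use different patients, so P(verdicts disagree) = a(1 − b) + b(1 − a).

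| MMF share | n per arm, with / without | a | b | Verdicts disagree |
|---|---|---|---|---|
| 10% | 12 / 113 | 13.3% | 76.2% | 69% |
| 15% | 19 / 106 | 18.8% | 73.5% | 65% |
| 20% | 25 / 100 | 23.6% | 71.0% | 61% |
| 25% | 31 / 94 | 28.3% | 68.3% | 58% |
| 30% | 38 / 87 | 33.6% | 64.9% | 55% |
| 40% | 50 / 75 | 42.4% | 58.4% | 51% |
| 50% | 62 / 63 | 50.5% | 51.2% | 50% |

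Example at 10%: 0.133 × 0.238 + 0.762 × 0.867 = 0.032 + 0.661 = 0.69. Simulation (20,000 runs) gives 69%, 62%, 55% and 50% at shares of 10%, 20%, 30% and 50%.

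**The specific pattern.** Significant without MMF and not significant with it has probability b(1 − a):

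- 15% on MMF: 0.735 × 0.812 = 60%
- 25% on MMF: 0.683 × 0.717 = 49%
- 40% on MMF: 0.584 × 0.576 = 34%

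**Other inputs, MMF shares 10% to 50%.**

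| Common effect, SD | Verdicts disagree |
|---|---|
| 25 mL, SD 100 mL | 41% to 47% |
| 25 mL, SD 140 mL | 28% to 30% |
| 12.5 mL, SD 70 mL | 28% to 30% |
| 40 mL, SD 70 mL | 73% at 10% MMF, falling to 20% at 50% |
| No effect | 2 × 0.05 × 0.95 = 9.5% |

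SD 100 and 140 mL are assumptions. SAP 4.5.2 reports that home FVC varied more than expected but gives no SD.

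**Four cells.** With assumed cell shares of 5/15/25/55%, the powers are 8.7%, 18.8%, 28.3% and 54.9%. The chance of a mixed set of verdicts is 1 − P(all significant) − P(none) = 1 − 0.003 − 0.240 = 76%. Four equal cells give 73%.

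**The missing contrast.** SE = 70 × √(2/n₁ + 2/n₂), and the 95% half-width is 1.96 × SE.

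| MMF share | SE (mL) | Half-width (mL) | Power for a 25 mL difference in effects |
|---|---|---|---|
| 10% | 30.1 | 59 | 13% |
| 20% | 22.1 | 43 | 20% |
| 30% | 19.2 | 38 | 25% |
| 50% | 17.7 | 35 | 29% |

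At 10%, unrounded sizes of 12.5 and 112.5 give 58 mL instead of 59. Under equal effects, a test of this contrast declares a difference in 4.8% to 5.1% of simulated trials.

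**The case against.** The strongest case on the other side has five parts.

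- **No inference is planned.** The trial is described as hypothesis-generating, the objective is exploratory, no decision rule is attached to these tests, and the forest plots show mean declines as well as test results. This stands. A reader might infer that the plan intends to declare effect modification from a split in p-values; the documents do not say so. It limits the seriousness, but the contrast is still missing.
- **The disagreement rate is conditional.** A reader might infer that the two tests will usually disagree whatever the data. That is not supported. The rate exceeds one half at 25 mL and SD 70 mL when MMF users are a minority, and the reported variability of home FVC makes SD 70 mL doubtful. At SD 140 mL the likeliest outcome (about 68% to 69%) is that neither test is significant. Nor is subgroup size the whole cause: with equal subgroups the rate is still 50%, through limited power and chance.
- **The test without MMF is inferred.** The t-test sentence in SAP 4.5.4 literally names only patients who received MMF. The other half follows from the stratification wording, the plural and the forest plots. If only MMF recipients were tested, nothing would be compared at all.
- **The objective is broader than effect modification.** Its wording concerns the role of MMF in ILD, and deaths, hospitalizations and safety are also summarised. It would be wrong to say that it is addressed by FVC t-tests alone.
- **The contrast would be imprecise.** This is correct, and is a reason to report an interval rather than rely on a test.

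**Conclusion.** The gap is real and minor. Version 3.0 of the SAP specifies no treatment-by-MMF term, no between-subgroup contrast and no interval for one. The listed subgroups do not include a plain MMF yes/no split.

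At the planning inputs, with 10% to 30% on MMF, verdicts would split in about 55% to 69% of trials with identical effects. That range rests on an assumed share, an assumed 5% level and the planning SD, and it falls as shown when the SD is larger or the effect smaller. Even at SD 140 mL it is more than five times the roughly 5% false-signal rate of a direct test.

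The opposite overreading should also be avoided: adding the contrast would not settle whether MMF matters. At SD 70 mL its half-width exceeds the whole planned 25 mL effect at every share considered.

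**What to change.** In SAP 4.5.4 and 4.5.7:

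1. Add MMF yes/no as a subgroup in its own right.
2. Fit a linear model of individual FVC decline with treatment, MMF, IPAF and treatment × MMF. In the random-slope model of 4.5.6, add treatment × MMF × time with its lower-order terms, including MMF × time.
3. Report the difference in treatment effect with its 95% CI in the home and site forest plots.
4. Label it descriptive and added after the primary analysis, which SAP 4.5.8 dates to March 2019.
5. State its expected precision, so that an interval covering zero is not read as absence of effect modification.
6. Correct the subgroup references from 4.5.6 to 4.5.7.

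Within-subgroup p-values may stay if intervals are shown beside them; dropping them is optional. The cost is one extra term in models of data already collected and one more forest-plot column.
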